All analyses will be conducted separately for each database, and will be carried out in a federated manner, allowing analyses to be run locally without sharing patient-level data. For each analysis, we will subsequently pool effect estimates across databases using random effect meta-analyses, I² for heterogeneity will be reported.

Cell counts <5 will be suppressed to comply with the database’s privacy protection regulations.

	Phase II C3-002 – Study Protocol	
	Author(s): [name], [name], [name]	Version: v2.1
		Dissemination level: Public

Objective 1 and 2: Effectiveness of 2nd COVID-19 vaccine booster dose in people with 1 previous booster dose

Study population

People with a 3rd-vaccine dose (1st booster dose) of Comirnaty or Spikevax will be included from the source population. Cohorts will be generated separately for Comirnaty and Spikevax, respectively.

Study inclusion: Sequential matching

Inclusion will be conducted in a sequential manner as follows.

For each calendar week starting from the day when a 4th vaccine dose (i.e. 2nd booster vaccine) became available/recommended in the respective country, people will be assigned to two cohorts: people who received a 2nd booster dose that week (“boostered”) and people who did not receive a 2nd booster (“non-boostered”).

Using the first day of the respective week as “preliminary” index date for non-boostered people, and the date of the 4th vaccine dose for boostered people, the following inclusion criteria will be applied:

- At least 365 days of data availability in the respective database
- At least 90days of time elapsed since the last vaccine dose
- At least 90days of time elapsed since the last record of a clinical diagnosis of COVID-19 or positive SARS-COV-2 test.

Among those people in the boostered and non-boostered cohorts who met the inclusion criteria, non-boostered people will be match 1:1 to a boostered person, based on key confounders and large-scale propensity scores using nearest neighbor matching, with caliper width 0.2 standard deviation.

Key confounders will comprise but are not limited to:

- Age (e.g. 5-year age bands)
- Sex (exact)
- Geographic location (exact)
- Previous vaccine brands (e.g. homologous or heterologous vaccination scheme)
- Time from previous vaccination
- History of conditions for prioritization for vaccination
- Immunocompromised status
- Previous COVID-19 diagnoses (>90days before index date)

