8.4 Follow-up

For all analyses, follow-up time will start from index date.

End of follow-up for each objective will be the end of a person’s observation time (i.e. date of data extraction, database availability or death), the date of their next vaccine dose, fixed duration or the date of the respective outcome event, whatever comes first

Table 8.4.1: Operational Definition of Time 0 (index date) and other primary time anchors

Study population name(s)	Time Anchor Description (e.g. time 0)	Number of entries	Type of entry	Washout window	Care Setting ¹	Code Type	Diagnosis position	Incident with respect to...	Measurement characteristics/ validation	Source of algorithm
1 dose only	Vaccination date 1 st dose	1	incident	All history	OP	RxNorm	n/a	vaccination	n/a	n/a
Complete primary vaccination course (2 doses)	Vaccination date 2 nd dose	1	n/a	21days	OP	RxNorm	n/a	n/a	n/a	n/a
3rd dose (monovalent or adapted/bivalent)	Vaccination date 3 rd dose	1	n/a	90days	OP	RxNorm	n/a	n/a	n/a	n/a
4th dose (monovalent or adapted/bivalent)	Vaccination date 4 th dose	1	n/a	90days	OP	RxNorm	n/a	n/a	n/a	n/a
4th dose (any monovalent)	Vaccination date 4 th dose	1	n/a	90days	OP	RxNorm	n/a	n/a	n/a	n/a
4th dose, (any adapted/bivalent boosters)	Vaccination date 4 th dose	1	n/a	90days	OP	RxNorm	n/a	n/a	n/a	n/a

OP = outpatient, n/a = not applicable

	Phase II C3-002 – Study Protocol	
	Author(s): [name], [name], [name]	Version: v2
		Dissemination level: Public

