8.5 Study Population with inclusion and exclusion criteria

The source population will comprise all subjects aged 12 years and older, with at least 365 days of data availability in the respective database before index date (ID) [ID defined as the date of the “latest” vaccine dose administered] AND data availability from 12/2020 onwards (i.e. the time when the roll-out of the vaccination campaign started) in the respective database will be included.

People will then be matched 1:1 based on the number of vaccines doses they received [exposure], with their matched counterparts having 1 vaccine dose less at the time of matching. Based on the index date of matched counterparts, the following inclusion criteria will be applied:

- At least 365 days of data availability in the respective database
- At least 90days of time elapsed since the last vaccine dose for >2 doses), at least 21days of time elapsed since the last vaccine dose for 2 doses and no previous vaccine dose recorded for 1st dose).
- At least 90days of time elapsed since the last record of a clinical diagnosis of COVID-19 or positive SARS-COV-2 test.

For analyses where diabetes mellitus or cardiovascular events are assessed as post-acute COVID-19 complications, people must not have had a record of the outcome within 365days before their index date for cardiovascular events, and no record anytime before index date for diabetes.

Operational definitions of Inclusion and Exclusion Criteria are provided in [Tables 8.5.1](#) and [8.5.2](#).

	Phase II C3-002 – Study Protocol	
	Author(s): [name], [name], [name]	Version: v2
	Dissemination level: Public	

Table 8.5.1. Operational Definitions of Inclusion Criteria

Criterion	Details	Order of application	Assessment window	Care Settings ¹	Code Type	Diagnosis position ²	Applied to study populations:	Measurement characteristics/validation	Source for algorithm
Observation period of 365day prior entry (all cohorts)	Study participants will be required to have 365 days prior history observed before contributing observation time	before	[-365, 0]	n/a	n/a	n/a	All individuals within the selected databases	n/a	n/a
Covid-19 vaccinated: 1 dose only	Exactly 1 Comirnaty/Spikevax vaccination record	after	n/a	OP	RxNorm	n/a			
Covid-19 vaccinated: Completed primary vaccination course	Exactly 2 vaccination records, with the latest being Comirnaty/Spikevax and at least 21days later than the 1st dose.								

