8.6.2. Outcomes

Primary outcomes of interest:

1. COVID-19 related hospitalisation
2. COVID-19 related death
3. All-cause mortality in the 3 months after discharge from a COVID-19 hospitalisation
4. All-cause mortality in the 6 months after discharge from a COVID-19 hospitalisation
5. Incidence of new-onset type 1 Diabetes Mellitus beyond the first 30d after SARS-CoV-2 infection
6. Incidence of new-onset type 2 Diabetes Mellitus beyond the first 30d after SARS-CoV-2 infection
7. Incidence of cardiovascular events (cerebrovascular disorders, dysrhythmias, ischemic and non-ischemic heart disease, pericarditis, myocarditis, heart failure and thromboembolic disease) in the 12 months after a SARS-CoV-2 infection.

Preliminary code lists are available in the appendix of this protocol for all outcomes.

SARS-CoV-2 infection and COVID-19

Positive test result for SARS-CoV-2

RT-PCR tests have high sensitivity and specificity for SARS-CoV-2. However, as a result of changes in the availability of population wide RT-PCR and home self-reported lateral flow tests during the Omicron period, it may not be possible to exclusively use RT-PCR tests when identifying positive test results in all datasets. All positive test results for SARS-CoV-2 observable in the database will therefore be included for the primary analysis, with documentation of what type of test it was to allow sensitivity analysis restricted to RT-PCR diagnosed patients as needed.

Clinical diagnosis of COVID-19

Whilst testing for SARS-CoV-2 was commonly performed in some of the countries that will be represented in this study, clinical diagnoses of COVID-19 were also made for many individuals. Diagnostic codes compatible with COVID-19 will therefore also be identified, with the recorded date being used in the analyses.

Hospitalization with COVID-19

Patients hospitalized with COVID-19 will be identified based on having a hospitalization along with a confirmatory diagnosis or test result of COVID-19 (both as defined above) within a time window from 21 days prior to admission up to three days following their admission. This time window has been chosen in accordance with previous studies commissioned by the EMA, and aimed to include those who had the diagnosis made prior to their hospitalization and to allow for a delay in test results or diagnoses to be made or recorded, while excluding individuals with hospital-acquired COVID-19.

COVID-19 related death

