COVID-19 related death will be defined as death within 28 days from the date of COVID-19 clinical diagnosis or positive SARS-CoV-2 test.

	Phase II C3-002 – Study Protocol	
	Author(s): [name], [name], [name]	Version: v2.1
	Dissemination level: Public	

All-cause mortality

[figure not shown]
Death from any cause will be assessed from the date of death recorded in primary care records or from linked mortality information.

Post-acute COVID-19 complications

New-onset type 1 Diabetes Mellitus following SARS-COV-2 infection

New onset type 1 diabetes following SARS-COV-2 infection will be defined e.g. as a new diagnosis of Type 1 diabetes or prescription of insulin without concomitant use of other antidiabetic drugs within 30days-365days following SARS-CoV-2 positive test or clinical COVID-19 diagnosis. People with a previous recording of diabetes of any type, including HbA1c >6.5%, will not be included for objectives 4 and 5.

Figure 8.6.2.1 Illustrates the algorithm for the outcome definition of New-onset type 1 Diabetes Mellitus following SARS-COV-2 infection

	Phase II C3-002 – Study Protocol	
	Author(s): [name], [name], [name]	Version: v2.1
		Dissemination level: Public

New-onset type 2 Diabetes Mellitus following SARS-COV-2 infection

New onset type 2 diabetes following SARS-COV-2 infection will be defined as e.g. a new diagnosis of Type 2 diabetes or initiation of an oral antidiabetic medicine (e.g. metformin) within 30days-365days following SARS-CoV-2 positive test or clinical COVID-19 diagnosis. People with a previous recording of diabetes of any type, including HbA1c >6.5%, will not be included for objectives 4 and 5.

Phenotypes for Type 1 and Type 2 Diabetes Mellitus will be developed and tested across all databases before using the definition in this study. Plausibility test will be conducted using CohortDiagnostics, including the review of patient characteristics (e.g. demographics, comorbidities and previous comedication) for people identified with new onset diabetes.

Cardiovascular events

Cardiovascular events will be evaluated as a composite outcome and stratified for relevant subgroups:

Major cardiovascular events (MACE): will be identified by diagnostic codes for heart failure, acute myocardial infarction, stroke, or the occurrence of sudden cardiac death.

Venous thromboembolic events: will be identified by diagnostic codes for pulmonary embolism or deep vein thrombosis.

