8.8.3 Objectives 1-2: Vaccine effectiveness to prevent severe infection

Objectives 1 and 2 will assess the effectiveness of a 4th COVID-19 vaccine dose in people with 3 vaccine doses.

Study population

All people with a 3rd vaccine dose of Comirnaty or Spikevax will be included from the source population. Cohorts will be generated separately for Comirnaty and Spikevax, respectively.

Study inclusion: Sequential matching

Inclusion will be conducted using a sequential matching design, with similar designs being used in previous studies assessing vaccine effectiveness. Previous research showed matching to adequately reduce measured confounding in vaccine effectiveness research when including key variables such as geographic location²⁴.

Matching process using key confounders and Propensity Scores

For each calendar week starting from the day when a 4th vaccine dose (i.e. 2nd booster vaccine) became available/recommended in the respective country, people will be assigned to two cohorts: people who received a 4th vaccine dose during that week and people who did not receive a 4th dose.

Using the first day of the respective week as “preliminary” index date for non-boostered people, and the date of the 4th dose for booster-vaccinated people, the following inclusion criteria will be applied:

	Phase II C3-002 – Study Protocol	
	Author(s): [name], [name], [name]	Version: v2.1
		Dissemination level: Public

- At least 365 days of data availability in the respective database
- At least 90days of time elapsed since the previous vaccine dose (i.e. the 3rd or 4th vaccine dose)
- At least 90days of time elapsed since the last record of a clinical diagnosis of COVID-19 or positive SARS-COV-2 test.

Among those people in the cohorts who received or not received a 4th dose and met the inclusion criteria, non-boostered people will be matched 1:1 to a person receiving their 4th dose, based on key confounders and large-scale propensity scores using nearest neighbor matching, with caliper width 0.2 standard deviation. Key confounders will comprise but are not limited to:

- Age (e.g. 5-year age bands)
- Sex (exact)
- Geographic location (exact)
- Previous vaccine brands (e.g. homologous or heterologous vaccination scheme)
- Time from previous vaccination
- History of conditions for prioritization for vaccination
- immunocompromised status
- previous SARS-CoV-2 diagnosis (>90days before index date)

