Large-scale propensity scores (PS) will be computed to estimate the probability of receiving a 4th vaccine dose. Covariates to be included in the large-scale PS will be selected from co-medications and comorbidities recorded prior to cohort-specific index dates. Among those, covariates with a prevalence below 0.5% in the study population will be omitted. Logistic regression with LASSO regularization will then be used for variable selection. The list of selected covariates will be manually screened by 2 epidemiologists/clinical domain experts to exclude potential instrumental variables.

The same procedure will be conducted in the calendar week after, with previously non-boostered people being allowed to be included in the booster cohort once they change exposure status. Non-boostered people can only be matched once to a booster counterpart during the whole study. With matching, non-boostered counterparts will be assigned the date of when the booster counterpart received their 4th vaccine dose as their “final” index date (index date for the matched pair).

All booster and matched non-boostered people from sequential weekly matching will be combined into the booster and non-boostered cohort for subsequent analyses. The study inclusion and sequential matching process is illustrated in [Figure 8.8.3.1](#) below.

[figure not shown]

	Phase II C3-002 – Study Protocol	
	Author(s): [name], [name], [name]	Version: v2.1
	Dissemination level: Public	

Figure 8.8.3.1 Study inclusion and sequential matching process

	Phase II C3-002 – Study Protocol	
	Author(s): [name], [name], [name]	Version: v2.1
		Dissemination level: Public

Follow-up

In the matched cohorts, people will be followed up from their index date until the earliest of

- End of their observation (i.e. date of data extraction, death)
- 2nd booster vaccination for unvaccinated group, 3rd booster for vaccinated group etc.
- COVID-19 related hospitalization or death, with outcome date being defined as the date of first COVID-19 diagnosis/positive test related to hospitalization or death.

Follow-up will be censored for the matched pair if one counterpart is censored, but not if one counterpart experiences the outcome.

Outcomes

The outcomes are defined in detail in section 8.6.2.

COVID-19 related hospitalization will be assessed for SIDIAP and IPCI. COVID-19 related death will be assessed for CPRD, IPCI and SIDIAP.

Statistical Analyses

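### Current inpatients are not excluded at the index date, so comparators can carry some admissions and deaths already under way into the first weeks of follow-up

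*Protocol*

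**What the plan says.** For Objectives 1 and 2 the entry conditions (Protocol, Abstract, section 8.8.3 and Tables 8.5.1 and 8.5.2) are a year of data, 90 days since the previous dose, and "At least 90days of time elapsed since the last record of a clinical diagnosis of COVID-19 or positive SARS-COV-2 test". None mentions current hospital stay. The matching list in 8.8.3 covers age, sex, location, vaccination history, prioritisation conditions, immunocompromise and earlier COVID-19. It is open-ended, but hospital status is not named.

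The date of the check is described in two ways:
- 8.8.3: "Using the first day of the respective week as “preliminary” index date for non-boostered people", after which "non-boostered counterparts will be assigned the date of when the booster counterpart received their 4th vaccine dose as their “final” index date".
- 8.5: "Based on the index date of matched counterparts, the following inclusion criteria will be applied".

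Section 8.4 adds that "For all analyses, follow-up time will start from index date", so there is no lag after the dose.

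On outcomes, section 8.6.2 accepts a hospitalisation as COVID-19 related if the diagnosis or test falls "within a time window from 21 days prior to admission up to three days following their admission". In 8.8.3 the event is dated not at admission but "with outcome date being defined as the date of first COVID-19 diagnosis/positive test related to hospitalization or death". For death, 8.6.2 states: "COVID-19 related death will be defined as death within 28 days from the date of COVID-19 clinical diagnosis or positive SARS-CoV-2 test".

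Section 8.8.6 plans no sensitivity analyses.

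**The concern.** The two members of a pair enter follow-up on the same day, but only one of them has just been dosed. It is a reasonable inference, though not a statement in the protocol, that few people are dosed while acutely ill. Comparators face no such filter and may be inpatients at time zero. If so, the arms differ on the first day in something that strongly predicts admission and death over the next few weeks, for a reason unrelated to vaccine protection.

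Objective 2 is the most exposed. It reads waning from hazard ratios in successive two-week windows, so an excess of comparator events confined to the first window looks like high early protection that then fades.

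**Working it through.** The plan gives no event count or expected bias, so there is no figure to reproduce. The check is to trace which people the rules let through and then illustrate the size.

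**Step 1: what the 90-day rule removes.** It removes anyone with COVID-19 recorded by the check date. Since the event is dated at the first COVID-19 record, an episode already recorded at the check is not carried in.

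**Step 2: what still passes.**
- Route (a), hospitalisation: a comparator is admitted on day -1 and first tests positive on day +1. There is no COVID-19 record at index, so the person is eligible. The test is two days after admission, inside the three-day limit, and the event is dated day +1. An admission that precedes time zero counts as a follow-up event.
- Route (b), death: a comparator in hospital for another illness at index tests positive later in the stay and dies within 28 days. If the test is more than three days after admission, the stay is not a COVID-19 hospitalisation, but the death is a COVID-19 death.

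**Step 3: the check date.** Under 8.8.3 a comparator is checked on the first day of the week and starts follow-up on the partner's dose date, up to six days later, with no stated re-check. Under 8.5 the check is at the matched index date. The two must be reconciled.

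**Step 4: general illustration (all inputs assumed).** Let f be the share of comparator events carried in, none in the dosed arm, all in window 1, with other events spread evenly over k two-week windows and true effectiveness (VE) constant at 50%.

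Overall VE = 1 - (1 - VE)(1 - f). First-window share f1 = f / (f + (1 - f)/k). First-window VE = 1 - (1 - VE)(1 - f1).

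| f | overall VE | f1, VE in window 1 (12 weeks, k=6) | f1, VE in window 1 (26 weeks, k=13) |
|---|---|---|---|
| 2% | 51.0% | 10.9%, 55.5% | 21.0%, 60.5% |
| 5% | 52.5% | 24.0%, 62.0% | 40.6%, 70.3% |
| 10% | 55.0% | 40.0%, 70.0% | 59.1%, 79.5% |

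Later windows read the true 50% in every row.

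**Step 5: route (a) alone (inputs assumed).** If a share q of COVID-19 admissions is first recorded d days after admission, the no-effect hazard ratio in the first 14 days is (14 - qd)/14:
- q = 20%, d = 1: 13.8/14 = 0.986.
- q = 100%, d = 0.5, 1, 1.5: 0.964, 0.929, 0.893.

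The carried-in share of first-window comparator events is qd/14, from 1.4% to 10.7%. The f = 2%, 12-week cell above (10.9%) is therefore already at the top of this range, and the larger rows are high cases for hospitalisation.

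**Step 6: route (b) alone (inputs assumed).** If a share p of comparators are inpatients with R times the hazard of COVID-19 death in the next weeks, and no dosed people are, the early no-effect hazard ratio is 1/(1 - p + pR):
- p = 0.3%, R = 20: 1/1.057 = 0.946
- p = 0.5%, R = 20: 1/1.095 = 0.913
- p = 1%, R = 20: 1/1.19 = 0.840
- p = 1%, R = 50: 1/1.49 = 0.671

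A true VE of 50% would read 52.7%, 54.3%, 58.0% and 66.4%, in the early period and for death only.

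**The case against.** A reader might infer that nothing screens comparators for illness, that dosed people are certain to be well, and that effectiveness is therefore materially inflated for both outcomes. The documents do not support that reading, for these reasons:

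- The 90-day rule removes recorded COVID-19, and events are dated at the first record.
- The three-day limit in 8.6.2 is meant to keep out hospital-acquired infection. An inpatient at index who tests positive later than that cannot have a COVID-19 hospitalisation in that stay, which pushes the other way for this outcome. Route (b) concerns death only.
- Patients diagnosed before admission fall inside the hospitalisation window too and add nothing to route (a), so a mean delay of 0.5 to 1.5 days across all admissions is a high assumption.
- Conditions and medications from the previous 30 days can enter the propensity score, and negative control outcomes are planned.
- Frail and prioritised people are also dosed, so p is not strictly zero in that arm.

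All of this stands and limits the size. It does not close the gap. Covariates below 0.5% prevalence are dropped, which could remove a marker of current illness. Empirical calibration is firm in the Abstract for Objectives 1 and 2 but only a possibility in 8.8.3, and neither text directs it at the first window.

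It is also fair to say that, on the stated dates, an inpatient rule has little to act on. Table 8.2.1 gives SIDIAP's data lock as 06/2022, while the Abstract starts the fourth-dose period on 01/08/2022. Those passages need reconciling, and the rule would matter for whichever data cut is used.

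**Conclusion.** The point holds in a limited form. Beyond the 90-day COVID-19 record rule, no criterion removes people in hospital on the index date, and two narrow routes let comparators bring in events already under way: late-tested admissions for hospitalisation, and other inpatients for death. The likely direction is some overstatement of effectiveness, concentrated in the first bi-weekly window, where it can imitate waning.

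The overall shift is probably small: 1 to 5 percentage points at a true 50% for f between 2% and 10%. The size cannot be fixed from the documents, because f, k, q, d, p and R are all assumptions and the good health of dosed people is an inference. This is a cheap improvement, not a flaw that invalidates the design.

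**What to change.** - In 8.5, 8.8.3 and Table 8.5.2: apply the criteria to both members of the pair on the final index date, and exclude anyone in hospital that day (admission date <= index date <= discharge date) in databases with admission data. This also settles the difference between 8.5 and 8.8.3.
- In 8.6.2: count a COVID-19 hospitalisation only if the admission date is after the index date.
- In 8.8.6: for databases without admission data, add a sensitivity analysis that leaves out the first one to two weeks of follow-up.

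The cost is protocol wording, a few lines of cohort code and a small loss of people. The inpatient rule works only where admissions are recorded. That is SIDIAP. For IPCI the passages conflict: the outcomes list in the Abstract says hospitalisation is unavailable, while later Abstract text, 8.2 and 8.8.3 say it will be assessed. They must be reconciled first.
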